8.1.3. Secondary Endpoint

The secondary endpoints include:

- The proportion of subjects who achieve HIV-1 RNA < 50 copies/mL at Weeks 96 and 144 as defined by the US FDA-defined snapshot algorithm
- The proportion of subjects who achieve HIV-1 RNA < 20 copies/mL at Weeks 48, 96 and 144 as defined by the US FDA-defined snapshot algorithm
- The change from baseline in log₁₀ HIV-1 RNA and CD4+ cell count at Weeks 48, 96, and 144
- The proportion of subjects who achieve HIV-1 RNA < 50 copies/mL at Weeks 48 OL and 96 OL as defined by Missing = Excluded and Missing = Failure algorithm
- The change from baseline in CD4+ cell count at Weeks 48 OL and 96 OL.

8.2. Analysis Conventions

8.2.1. Analysis Sets

8.2.1.1. All Randomized

The randomized analysis set includes all subjects who are randomized into the study. This is the primary analysis set for by-subject listings.

8.2.1.2. Efficacy

8.2.1.2.1. Full Analysis Set (FAS)

The primary analysis set for efficacy analyses is defined as full analysis set (FAS), which will include all subjects who (1) are randomized into the study and (2) have received at least 1 dose of study drug. Subjects will be grouped according to the treatment to which they were randomized.

8.2.1.2.2. Per-Protocol (PP) Analysis Set

The secondary analysis set for efficacy analyses is defined as per-protocol (PP) analysis set, which will include all subjects who (1) are randomized into the study, (2) have received at least 1 dose of study drug, and (3) have not committed any major protocol violation, including the violation of key entry criteria. Subjects will be grouped according to the treatment they actually received.

Subjects meeting any of the following criteria will be excluded from the Week 48 PP analysis set:

- 1) Subjects who do not have on-treatment HIV-1 RNA in the Week 48 analysis window, except when missing data is due to discontinuation of study drug for lack of efficacy.
- 2) Subjects who do not meet the inclusion criterion that the screening genotype report must show sensitivity to FTC, TFV.
- 3) Subjects who meet the exclusion criterion for receiving ongoing therapy with any of the medications listed in the table in protocol Section 4.3 including drugs not to be used with GS-9883, FTC, TAF, and DTG.
- 4) Nonadherence to study drug: subjects with adherence rate for active study drug up to the Week 48 Visit below the 2.5th percentile

8.2.1.3. Safety

The primary analysis set for safety analyses is defined as safety analysis set, which will include all subjects who (1) are randomized into the study and (2) have received at least 1 dose of study drug. All the data collected up to 30 days after subjects permanently discontinue their study drug will be included in the safety summaries, unless specified otherwise. Subjects will be grouped according to the treatment they actually received.

8.2.1.4. Pharmacokinetics

CCI

8.2.1.4.2. Pharmacokinetic (PK) Analysis Set

The primary analysis set for general PK analyses is defined as the PK analysis set, which will include all subjects who (1) are randomized into the study, (2) have received at least 1 dose, and (3) have at least 1 nonmissing PK concentration data for any the analyte of interest reported by the PK lab.

8.2.1.5. All GS-9883/F/TAF Analysis Set

All GS-9883/F/TAF analysis set will include all subjects who (1) are randomized into the study and (2) have received at least 1 dose of the blinded GS-9883/F/TAF or OL GS-9883/F/TAF. Subjects will be grouped into two groups: (1) All GS-9883/F/TAF group, including all subjects who randomized into GS-9883/F/TAF and received at least 1 dose of GS-9883/F/TAF; (2) DTG + F/TAF to GS-9883/F/TAF group, including all subjects who randomized to DTG + FTAF in the double-blinded phase and received at least 1 dose of OL GS-9883/F/TAF in the extension phase. This is the primary analysis set for the all GS-9883/F/TAF efficacy and safety analyses.

8.3. Data Handling Conventions

HIV-1 RNA results of “No HIV-1 RNA detected” and “<20 cp/mL HIV-1 RNA Detected” will be imputed as 19 copies/mL for analysis purpose. Logarithm (base 10) transformation will be applied to HIV-1 RNA levels for efficacy analysis.

Natural logarithmic transformation of plasma concentrations and PK parameters will be applied for PK analysis.

Laboratory data that are continuous in nature but are less than the lower limit of quantitation or above the upper limit of quantitation will be imputed to the value of the lower or upper limit plus or minus one significant digit, respectively (eg, if the result of a continuous laboratory test is < 20, a value of 19 will be assigned).

Missing data can have an impact upon the interpretation of the trial data. In general, values for missing data will not be imputed. However, a missing pre-treatment laboratory result would be treated as normal (ie, no toxicity grade) for the laboratory abnormality summary.

All available data for subjects that do not complete the study will be included in data listings.

8.4. Demographic Data and Baseline Characteristics

Demographic and baseline characteristics will be summarized using standard descriptive methods including sample size, mean, SD, median, Q1, Q3, minimum, and maximum for continuous variables and frequency and percentages for categorical variables.

Demographic data will include sex, race, ethnicity, and age.

Baseline characteristics will include body weight, height, body mass index, eGFR, HIV-1 infection, and enrollment distribution by randomization stratum will be summarized.

For categorical demographic and baseline characteristics, the Cochran–Mantel–Haenszel (CMH) test will be used to compare treatment groups. For continuous demographic and baseline characteristics, the Wilcoxon rank sum test will be used to compare treatment groups.

8.5. Efficacy Analysis

8.5.1. Primary Analysis

8.5.1.1. Primary Efficacy Endpoint

The primary efficacy endpoint is the proportion of subjects who achieve HIV-1 RNA < 50 copies/mL at Week 48 as determined by the US FDA-defined snapshot algorithm. The primary analysis of the efficacy endpoint will be based on the FAS.

8.5.1.2. US FDA-defined Snapshot Algorithm

The analysis window at Week 48 is defined as from Study Day 295 to Study Day 378. All HIV-1 RNA data collected on-treatment (ie, including data collected up to 1 day after the last dose date of study drug) will be used in the snapshot algorithm. Virologic outcome will be defined as the following categories:

- **HIV-1 RNA < 50 copies/mL:** this includes subjects who have the last available HIV-1 RNA < 50 copies/mL in the Week 48 analysis window while on randomized treatment
- **HIV-1 RNA ≥ 50 copies/mL:** this includes subjects
 - a) Who have the last available HIV-1 RNA ≥ 50 copies/mL in the Week 48 analysis window while on randomized treatment, or
 - b) Who do not have on-treatment HIV-1 RNA data in the Week 48 analysis window and
 - i) Who discontinue study drug prior to or in the Week 48 analysis window due to lack of efficacy, or
 - ii) Who discontinue study drug prior to or in the Week 48 analysis window due to reasons other than adverse event (AE), death, or lack of efficacy and have the last available HIV-1 RNA up to 1 day after the premature discontinuation of the study drug ≥ 50 copies/mL

- **No Virologic Data in the Week 48 analysis window:** this includes subjects who do not have on-treatment HIV-1 RNA data in the Week 48 analysis window because of the following:
 - a) Discontinuation of study drug prior to or in the Week 48 analysis window due to AE or death (regardless of whether the last available HIV-1 RNA up to 1 day after the premature discontinuation of the study drug < 50 copies/mL or not) or,
 - b) Discontinuation of study drug prior to or in the Week 48 analysis window due to reasons other than AE, death, or lack of efficacy (eg, withdrew consent and loss to follow-up) and the last available HIV-1 RNA up to 1 day after the premature discontinuation of the study drug < 50 copies/mL or,
 - c) Missing data during the window but on study drug.

8.5.1.3. Analysis of Primary Efficacy Endpoint

The null hypothesis is that the proportion of subjects achieving HIV-1 RNA < 50 copies/mL (as defined by the US FDA-defined snapshot algorithm) at Week 48 in GS-9883/F/TAF is at least 12% lower than the response rate in DTG + F/TAF; the alternative hypothesis is that the response rate in GS-9883/F/TAF is less than 12% lower than that in DTG + F/TAF.

Non-inferiority will be assessed using the conventional confidence interval approach. The point estimate of treatment difference (GS-9883/F/TAF group – DTG + F/TAF group) and the associated 2-sided 95% confidence interval will be constructed using a normal approximation method based on stratum-stratified Mantel-Haenszel proportions, where stratification factors include baseline HIV-1 RNA level ($\leq 100,000$ copies/mL, vs. $> 100,000$ copies/mL) and region (US vs. Ex-US). Note that to avoid small or missing cells in analysis strata, CD4+ cell count is not stratified in the analysis because HIV-1 RNA and CD4+ cell count are highly correlated.

If non-inferiority of GS-9883/F/TAF to DTG + F/TAF is established, the lower bound of the 95% CI will be compared to 0; if the lower bound of the 95% CI is greater than 0, then superiority of GS-9883/F/TAF over DTG + F/TAF will be established.

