5. INVESTIGATIONAL MEDICINAL PRODUCTS

5.1. Randomization, Blinding and Treatment Codes

Subjects will be assigned a screening number at the time of consent. **Randomization and Day 1 visits cannot occur until the Investigator has received the results of the screening genotype report and subject eligibility has been confirmed.**

Once eligibility has been confirmed and prior to or during the Day 1 visit, the Investigator or designee will randomize the subject using the Interactive Web Response System (IWRS). Once a subject number has been assigned to a subject, it will not be reassigned to any other subject. The subject number assignment and randomization may be performed up to 3 days prior to the in-clinic Day 1 visit provided that all screening procedures have been completed and subject eligibility has been confirmed.

Subjects will be randomized in a 1:1 ratio to Treatment Group 1 or Treatment Group 2.

Randomization will be stratified by HIV-1 RNA level ($\leq 100,000$ copies/mL, $> 100,000$ to $\leq 400,000$ copies/mL, or $> 400,000$ copies/mL) at screening, CD4+ cell count (< 50 cells/ μ L, $50 - 199$ cells/ μ L, or ≥ 200 cells/ μ L) at screening and region (US vs. Ex-US) at randomization.

The IWRS will assign study drug bottle numbers of blinded FDC of GS-9883/F/TAF + Placebo to match DTG + F/TAF FDC, or DTG + F/TAF FDC + Placebo to match FDC of GS-9883/F/TAF at each study visit for each subject.

At the End of Blinded Treatment Visit the IWRS will assign open label GS-9833/F/TAF/FDC

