8.5.2. Secondary Analyses

The proportion of subjects who achieve HIV-1 RNA < 50 copies/mL at Weeks 96 and 144 and the proportion of subjects who achieve HIV-1 RNA < 20 copies/mL at Weeks 48, 96 and 144, as defined by the US FDA-defined snapshot algorithm, will be analyzed using the same method as for the primary efficacy endpoint.

The changes from baseline in log₁₀ HIV-1 RNA and CD4+ cell count at Weeks 48, 96, and 144 will be summarized by treatment using descriptive statistics. The differences in changes from baseline in log₁₀ HIV-1 RNA and CD4+ cell count between 2 treatments groups and the associated 95% confidence intervals will be constructed using ANOVA models, including treatment (GS-9883/F/TAF vs. DTG + F/TAF), baseline HIV-1 RNA level ($\leq 100,000$ copies/mL vs. $> 100,000$ copies/mL), and region (US vs. Ex-US) as fixed effects in the model.

In addition, missing CD4+ cell count will be imputed using Last Observation Carried Forward (LOCF) method and analyzed similarly.

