8.9. Sample Size

A total of approximately 600 HIV-1 infected subjects, randomized in a 1:1 ratio to 2 treatment groups (300 subjects per treatment group), achieves at least 95% power to detect a non-inferiority margin of 12% in Week 48 response rate (HIV-1 RNA < 50 copies/mL as defined by the US FDA-defined snapshot algorithm) difference between the 2 treatment groups. For the sample size and power computations, it is assumed that both treatment groups have a response rate of 91% (based on Gilead Studies GS-US-292-0104 and GS-US-292-0111), that the non-inferiority margin is 12%, and that the significance level of the test is at a one-sided 0.025 level. Sample size and power calculations were made using the statistical software package nQuery Advisor (Version 6.0).

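### The CD4-change ANOVA (Protocol 8.5.2) has no baseline CD4 term, and the sparse-cell reason given for the primary analysis does not cover that omission

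*Protocol*

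**What the plan says.** Protocol Section 5.1: "Randomization will be stratified by HIV-1 RNA level" in three levels, by screening CD4+ count in three levels (below 50, 50 to 199, 200 or more cells/µL), and by "region (US vs. Ex-US) at randomization". That makes 3 × 3 × 2 = 18 randomization strata.

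Protocol Section 8.5.1.3 builds the primary interval by a "normal approximation method based on stratum-stratified Mantel-Haenszel proportions", with RNA in two levels and region, so 4 analysis strata. Two reasons for leaving CD4 out are on the page, in one sentence: sparse cells ("Note that to avoid small or missing cells in analysis strata, CD4+ cell count is not stratified in the analysis") and redundancy with RNA ("CD4+ cell count is not stratified in the analysis because HIV-1 RNA and CD4+ cell count are highly correlated"). No correlation figure is given.

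Protocol Section 8.5.2 says that the treatment differences in change in log10 HIV-1 RNA and in CD4+ count "will be constructed using ANOVA models, including treatment", baseline RNA category and region as fixed effects. The CD4 analysis is repeated with missing values carried forward (LOCF). The synopsis gives the same model. Neither place has a CD4 term or a reason for its absence.

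Baseline CD4 is available: the count is taken at screening and on Day 1 (Protocol Sections 6.2.1 and 6.2.2).

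The supplied SAP covers the final analysis only. Its Sections 6 and 6.2.1 state that the Week 48, 96 and 144 endpoints have been analysed and refer the methods to earlier plans, which were not supplied. Its own CD4 summaries (Section 6.3.2.2) are descriptive, without comparison.

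**The concern.** For a continuous change score, the baseline value of the same variable is the usual first covariate. The plan's RNA-change model contains the outcome's own baseline, at least in two categories. The CD4-change model contains none.

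Two things are lost. If baseline CD4 predicts change, the variation it explains stays in the residual and the interval is wider than it need be. And any chance difference in mean baseline CD4 between arms passes into the estimated treatment difference. Stratified randomization limits that only coarsely: the top stratum is everything from 200 cells/µL up, and in the Phase 2 study (Protocol Section 1.2.3.3) the first quartile was already 316, so about three quarters or more of subjects would share one CD4 stratum.

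At stake is the precision of a named secondary endpoint. The primary conclusion is not affected.

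**Working it through.** **Inputs.** Phase 2, Week 24 (Protocol Section 1.2.3.3): SD of CD4 change 177.8 (GS-9883 arm, 65 randomized) and 163.2 (DTG arm, 33 randomized); reported 95% CI for the adjusted difference −35 to 113; baseline SD 190.9 (GS-9883 arm). This trial (Protocol Section 8.9): 300 per arm, 91% response in both arms, 12-point margin; "the significance level of the test is at a one-sided 0.025 level". The correlation r between baseline CD4 and change is not in the documents and is varied.

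**1. Check that the SD reproduces a reported interval.** Pooled SD = √[(64 × 177.8² + 32 × 163.2²)/96] = 173.1. SE = 173.1 × √(1/65 + 1/33) = 37.0. Half-width = 1.985 × 37.0 = 73.4. Reported: (113 + 35)/2 = 74. The SD is a usable guide.

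**2. Half-width in this trial without baseline CD4.** SE = 177.8 × √(2/300) = 14.52; half-width = 1.96 × 14.52 = 28.45 cells/µL. (With SD 163.2 it is 26.1.) This ignores missing data and anything RNA category and region explain.

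**3. With continuous baseline CD4.** Half-width = 28.45 × √(1 − r²):

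- r = 0: 28.45 (no change)
- r = 0.3: 28.45 × 0.954 = 27.1 (4.6% narrower)
- r = 0.4: 28.45 × 0.917 = 26.1 (8.3% narrower)
- r = 0.5: 28.45 × 0.866 = 24.6 (13.4% narrower)

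Using CD4 category instead, with an assumed extra R² of 0 to 5%, gives 28.5 to 27.7 (0 to 2.5% narrower). The continuous covariate is the better choice.

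**4. Chance imbalance.** Ignoring stratification, the SE of the baseline difference is 190.9 × √(2/300) = 15.6 cells/µL. An imbalance of one SE shifts the unadjusted difference in change by slope × 15.6, with slope of size r × 177.8/190.9. For r = 0.3 that is 0.279 × 15.6 = 4.4 cells/µL; for r = 0.5, 0.466 × 15.6 = 7.3 cells/µL.

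**5. The primary endpoint, for contrast.** The plan claims at least 95% power. SE = √(2 × 0.91 × 0.09/300) = 0.02337; power = Φ(0.12/0.02337 − 1.96) = Φ(3.18) = 99.9%, so the claim is met. Half-width = 1.96 × 0.02337 = 4.58 points.

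- Adding CD4, computed analytically under assumed response rates in the two lower CD4 groups: 4.57 to 4.58 (85% and 88%), 4.49 to 4.56 (75% and 82%), 4.27 to 4.51 (60% and 75%, an extreme case). That is 0 to 2% in the first two cases and at most 7% in the last.
- Simulation of 600 subjects in permuted blocks within the 18 strata, with 12% below 200 cells (assumed), going from 4 to 8 strata by adding CD4 split at 200, for a smaller and a larger assumed CD4 effect: half-width with Sato variance 4.559 to 4.546 and 4.558 to 4.483; with plain variance 4.533 to 4.475 and 4.529 to 4.399; with an add-half variance 4.686 to 4.779 and 4.681 to 4.699, which is wider.
- The actual sampling SD of the estimate hardly moved: 0.0232 to 0.0233 and 0.0225 to 0.0225.

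**The case against.** The case for leaving things alone is fair. The CD4-change analysis is secondary, its model is pre-specified, and under randomization the estimate without baseline CD4 is still unbiased with a valid interval. The gain rests on a correlation that the documents do not report. RNA category is in the model, and if RNA and CD4 are as closely related as Section 8.5.1.3 says, some of baseline CD4 is already captured. The analyses are also done, and an earlier SAP may have added the term. All of this stands as a limit on size and timing. It does not supply a reason for the omission: a two-level RNA factor can carry only part of a continuous CD4 count, the correlation is unquantified, and avoiding small cells is irrelevant to a single covariate in an additive model.

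A reader might go further and infer that leaving CD4 out of the Mantel-Haenszel strata wastes the stratified randomization and makes the primary interval too wide. The documents do not support that. The omission is disclosed with two reasons. The balance from stratified randomization is already in the estimate, whose sampling SD is unchanged when CD4 is added; only the estimated SE can differ, and whether it shrinks depends on the variance formula, which the protocol does not fully specify. Sparse cells are a real consideration: Phase 2 quartiles suggest about 27 to 71 of 600 subjects below 200 cells, and with all three CD4 levels (12 strata) the simulations averaged 2.3 to 3.8 strata with fewer than 5 subjects in an arm. The 8-stratum split is much less sparse (0.3 such strata on average in the simulations shown), so it is feasible, but it buys almost nothing against a 12-point margin.

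**Conclusion.** The point holds for the CD4-change models only. Omitting baseline CD4 there is unexplained and costs an estimated 5% to 13% of a half-width of about 28.5 cells/µL if the correlation between baseline and change is 0.3 to 0.5, and close to nothing if it is zero. It also leaves chance baseline imbalance unadjusted, worth roughly 4 to 7 cells/µL per SE of imbalance under the same assumption. These figures assume that the Phase 2 Week 24 SDs carry over, 300 evaluable subjects per arm, and a linear relation common to both arms. The unadjusted analysis is less efficient, not wrong.

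For the primary endpoint the omission is a defensible trade-off and no conclusion turns on it. This is a minor improvement.

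**What to change.** In Protocol Section 8.5.2 and the synopsis, add continuous baseline CD4+ count as a covariate (ANCOVA) to the CD4-change models at Weeks 48, 96 and 144, including the LOCF version. Keep treatment, RNA category and region.

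Since the SAP reports those analyses as complete, first check whether the earlier SAPs already contain the term. If they do not, run the ANCOVA as a labelled supplementary analysis beside the planned one, and carry the wording into later protocols of this design. The cost is one model term and one degree of freedom; no new data are needed.

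Leave the primary strata as they are. A Mantel-Haenszel analysis with CD4 split at 200 cells/µL, with a pooling rule for cells empty in one arm, is at most an optional sensitivity analysis.

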8.5.2. Secondary Analyses

The proportion of subjects who achieve HIV-1 RNA < 50 copies/mL at Weeks 96 and 144 and the proportion of subjects who achieve HIV-1 RNA < 20 copies/mL at Weeks 48, 96 and 144, as defined by the US FDA-defined snapshot algorithm, will be analyzed using the same method as for the primary efficacy endpoint.

The changes from baseline in log₁₀ HIV-1 RNA and CD4+ cell count at Weeks 48, 96, and 144 will be summarized by treatment using descriptive statistics. The differences in changes from baseline in log₁₀ HIV-1 RNA and CD4+ cell count between 2 treatments groups and the associated 95% confidence intervals will be constructed using ANOVA models, including treatment (GS-9883/F/TAF vs. DTG + F/TAF), baseline HIV-1 RNA level ($\leq 100,000$ copies/mL vs. $> 100,000$ copies/mL), and region (US vs. Ex-US) as fixed effects in the model.

In addition, missing CD4+ cell count will be imputed using Last Observation Carried Forward (LOCF) method and analyzed similarly.

